All participants will be asked about depressive symptoms every two weeks for the first 12 weeks over the telephone or in-person. Participants will also be asked to complete more comprehensive telephone and in-person follow-up assessments at 6, 12, and 24 weeks (as shown in Figure 1 and Table 1). During these assessments, participants will be asked to complete the same questionnaires as during the baseline assessment and several additional measures dependent on the assessment as identified in Table 1 focused on patient receptivity and medication/treatment history.

All assessment sessions will be led by research assistants blind to condition and take place primarily (unless requested otherwise) via the telephone except the baseline, 12, and 24 weeks (see Table 1). The 12-week assessment will occur over the telephone if unexpected circumstances prevents the Veteran from being able to come in to the medical center. All research assistants will track any non-study care given to participants as that may be a potential confounding variable to our examination of treatment effect⁸⁸.

At baseline, 12, and 24 week sessions, information will be collected from the medical chart of each participant regarding his/her current medical problem list, medications, engagement with mental health care, including types of interventions that they may or may not have participated in during the study as monitored by the VA electronic medical record system.

Treatment As Usual Condition

TAU will involve the Veteran receiving an appointment with the integrated MHP at their primary care clinic. At this encounter, the MHP can choose to deliver whatever interventions they deem necessary. In addition, the MHP and Veteran can work together to identify whether and when they would like to meet again during the 12-week period of the active portion of the study. As recommended by Freeland et al⁸⁸, it is unnecessary to force the TAU condition to have the same amount of attention unless the purpose is to examine specific and nonspecific effects, which is not the case in this study.

BA-PC Intervention

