Intervention Description. A revised 4-session BA-PC manual was created with the help of [name], one of the original authors of the Brief Behavioral Activation Manuals (see Appendix 4). BA-PC will focus on 1) providing feedback regarding his/her experience of symptoms of depression, including the severity; 2) helping the Veteran understand the theoretical foundation for BA, the research behind it, and why it will help reduce symptoms of depression; 3) identifying activities (or lack thereof) within the Veteran's life that may be helping to maintain depressive symptoms as well as any current behaviors that might be eliciting positive reinforcement of depressive behaviors; and 4) identifying new value-based activities that may elicit positive affect within a variety of major life domains (e.g., family, physical, etc.).

Patient Treatment Adherence. A fundamental component of BA is establishing specific measurable goals regarding his/her engagement in activities at the end of each session. Therefore, patient adherence to the BA intervention can be monitored by examining the proportion of the number of goals completed versus the number of goals identified as homework by the interventionist and patient at the end of each session. Then, individual patient adherence can be calculated for each session and overall patient adherence can be calculated for each intervention condition. These calculations will help us understand basic patient adherence to the modified brief forms of BA-PC, which will be used as an indirect reflection of patient receptivity.

Therapists & Therapists Training. Advanced-level clinical psychology graduate students or Masters-level MHPs working as research assistants will implement the 4-session format BA-PC. They will participate in a 2-day workshop to establish training in BA-PC led by Drs. [name] and [name]. Each research assistant will have to demonstrate proficiency within a role-play of BA-PC, observed by Drs. [name] and [name]. All BA-PC intervention sessions will be audio-taped and [name] will meet weekly with the research assistants to provide supervision of the BA-PC based on review of audio-taped sessions, session materials, and ad hoc supervision issues raised by research assistants. In addition, [name] will also provide monthly telephone supervision regarding the implementation of BA-PC.

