procedures. [name] will meet regularly with the research coordinator and staff to review monitoring procedures and ensure all efforts are being taken to minimize risks to participants.

To help monitor safety issues, we will have an independent Data Safety Monitoring Board (DSMB). As described below, we will track all negative outcomes and incidents as well as conduct interim data analysis every 12 months after the study has started. The study design will be significantly modified (and even screening stopped) on the advice of the DSMB that the study is creating potential harm to our participants.

Both co-PIs will regularly oversee all aspects of the study, including participant recruitment, informed consent, data collection, management, and analysis, as well as regularly assess the risk/benefit ratio associated with participation in the study. As a result, all research staff will participate in an intensive training to help them understand the importance of reducing the risk for participants and learning how to recognize and report any adverse event or serious adverse event to Drs. [name] or [name]. Serious adverse events (SAE) may include: death, hospitalization due to worsening depressive symptoms or suicidal ideation, or all life threatening or disabling/incapacitating events among research participants. Adverse events may include (but is not limited to): physical injuries, worsened physical or mental health, or inadvertent disclosure of confidential research information.

In the event of a SAE, the co-PIs will immediately communicate with the DSMB and Institutional Review Boards, followed by a written report in 24 hours. Jointly, we will make a decision whether there is sufficient evidence to necessitate suspension of data collection, further IRB review, modification of the protocol, or other changes to reduce potential risk to participants. Resumption of the study shall be based on the concurrence of the co-PIs, the chairperson of the IRBs, and the DSMB.

In the event that an adverse event that is not an SAE is reported to the co-PIs, they will discuss the event with the DSMB. Immediate evaluation will occur to determine if any extra steps can be taken to minimize the likelihood of that type of adverse event occurring again. If changes can be made, a report/amendment will be written and submitted to the DSMB and Institutional Review Boards.

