- i. Review and approve, disapprove, or suggest modifications to the study protocols and/or consent documents to assure both scientific integrity and study adherence to human subject protection policies.
- ii. Monitor, provide feedback, and report on scientific and ethical issues related to study implementation for the protection of human subjects and advise on ethical issues related to adverse events. The DSMB will

monitor adverse event reports for purposes of determining whether their nature, frequency and severity are consistent with expectations.

The DSMB, in coordination with the co-PIs, will report to the VA IRBs any unanticipated problems involving risks to subject.

The DSMB can recommend remedies or other appropriate actions such as introducing new monitoring protocols, altering inclusion or exclusion criteria, or recommending changes in the informed consent documents.

- iii. Ensure that the study protocol maintains patients' confidentiality in a manner that is appropriately balanced with issues of clinical care and safety.
- iv. Monitor data regarding effectiveness. The DSMB will review data for outcomes by treatment group. If differences in results between groups appear to be clinically significant, the DSMB will review whether the clinical trial should continue with or without further enrollment of new subjects. The DSMB has the authority to halt the trial as needed.
- v. Monitor data management activities. The DSMB may ask to review data relevant to quality control. The DSMB will review requests for interim analyses and approve, disapprove, require additional information, or defer decisions.

At a minimum, the DSMB will convene on an annual basis throughout the study. During the first year, the DSMB will convene after the first 4 months of participant recruitment. DSMB meetings will be held in-person or via video teleconference. The Board Chair and co-PIs will decide upon the format of the meetings. Additional meetings or telephone conferences will be held on the recommendation of the DSMB. The Board Chair and the co-PIs will determine meeting logistics based upon clinical urgency and the availability of DSMB members.

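### Adverse events are captured through research staff who treat one arm only, with no standard question or AE-directed chart search, so any comparison of adverse events by arm is open to ascertainment bias

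*Combined protocol and SAP*

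**What the plan says.** Route of reporting. Under Data Safety and Monitoring Plan (Data Safety), "all research staff will participate in an intensive training", which includes "learning how to recognize and report any adverse event or serious adverse event" to the principal investigators, who inform the DSMB. The same section promises to track negative outcomes, but what follows covers definitions, timelines and DSMB duties. It describes no AE question, form or search, and Table 1 has no AE row.

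Who treats each arm. Under Therapists & Therapists Training, graduate students or "Masters-level MHPs working as research assistants will implement the 4-session format BA-PC". A study lead "will meet weekly with the research assistants to provide supervision of the BA-PC based on review of audio-taped sessions". In the other arm, "TAU will involve the Veteran receiving an appointment with the integrated MHP at their primary care clinic". No AE training or reporting duty is stated for those clinic providers. Under Therapist Treatment Fidelity, a research assistant brings and collects the recorder at TAU sessions, and raters score the recordings for treatment content and shared decision-making.

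What is equal. Under Assessments, blinded research assistants contact both arms every two weeks to week 12 and again at week 24, and non-study care is tracked. At baseline and weeks 12 and 24, chart data are taken "regarding his/her current medical problem list, medications, engagement with mental health care". Under Patient Safety, PHQ-9 item 9 is asked at every assessment, with further suicide-risk assessment as follow-up.

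Use of the reports. The DSMB is to "monitor adverse event reports for purposes of determining whether their nature, frequency and severity are consistent with expectations". It also reviews outcomes by treatment group and can halt the trial.

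**The concern.** An AE that nobody asks about is recorded only if the participant mentions it to someone who knows to report it. In BA-PC, each therapy session is such an occasion, and weekly supervision carries what is said to the study leads. In TAU, the same remark goes to a clinic provider who has no stated duty to pass it on. With equal true rates, BA-PC could therefore accumulate more reports.

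The DSMB can stop or change the study on grounds of harm. An excess produced by extra listening could be read as a harm signal against BA-PC, and a real safety advantage of BA-PC could be hidden. With 72 participants per arm and few events, a handful of additional reports can change the impression.

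**Working it through.** The plan states no AE rate, detection probability or power for harm, so there is no figure to reproduce. The check has two parts.

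**1. Count of scheduled contacts with AE-trained staff**

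Inputs: assessments at weeks 2, 4, 6, 8, 10, 12 and 24 in both arms (Table 1); four BA-PC sessions to be completed by week 12 (Intervention Format). TAU therapy sessions count as zero because no AE duty is given to the provider, to the research assistant handling the recorder, or to the raters.

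- To week 12: TAU 6; BA-PC 6 + 4 = 10.
- To week 24: TAU 7; BA-PC 7 + 4 = 11.

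Ten and eleven are maxima, since participants may attend fewer sessions.

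**2. Illustration of the possible effect to week 12**

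Assume an event is present throughout, each contact leads to a report with probability q, contacts are independent, and true rates are equal. Then P(reported) = 1 − (1 − q)^k, with k = 6 or 10. The values of q are assumptions; the documents give none.

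| q (assumed) | TAU: 1 − (1 − q)^6 | BA-PC: 1 − (1 − q)^10 | Ratio |
|---|---|---|---|
| 0.05 | 0.265 | 0.401 | 1.51 |
| 0.10 | 0.469 | 0.651 | 1.39 |
| 0.20 | 0.738 | 0.893 | 1.21 |
| 0.30 | 0.882 | 0.972 | 1.10 |
| 0.50 | 0.984 | 0.999 | 1.01 |

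In participants, with 72 per arm (Study Population) and an assumed true AE rate of 20%, 72 × 0.20 = 14.4 per arm have an event.

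- q = 0.10: 14.4 × 0.469 = 6.7 reported in TAU and 14.4 × 0.651 = 9.4 in BA-PC. The approximate chance of a nominally significant excess in BA-PC (two-sided 0.05 test of two proportions) is 10%.
- q = 0.50: 14.2 and 14.4 reported; the chance is about 3%.
- With no ascertainment difference, the chance in that direction is 2.5%.

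**Which events are exposed.** The ratio approaches 1 for events that the shared contacts detect well. Worsening mood and suicidal ideation belong here, because the PHQ-9 is given at every assessment and the SSI at weeks 6, 12 and 24 in both arms. Physical injuries and other worsened physical health are on the plan's AE list but have no matching question, so they sit nearer the top of the table.

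**With common ascertainment.** If comparisons use only the shared assessments and a shared chart search, scheduled opportunities are 6 versus 6 to week 12 and 7 versus 7 to week 24. The expected ratio is 1.00 when true rates are equal.

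**The case against.** The strongest reply is that the plan states no by-arm AE comparison. The DSMB compares AE reports with expectations, the annual AE summary has no stated split by arm, and review by group appears only for outcomes, under effectiveness. This stands: a reader might infer that a planned harm comparison is already biased, and the documents do not support that. What remains is that a board able to halt the trial for harm, and shown outcomes by group, may well look at AEs by group too, and nothing makes those counts comparable.

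Second, much ascertainment is equal: blinded mood and suicide-risk assessment, tracking of non-study care, treatment history at weeks 12 and 24, and chart review. This also stands, and it rules out saying that no equal chart review exists. The gap is that none of these sources is linked to AE recording and that the listed chart fields name neither admissions nor deaths.

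Third, the ratios rest on an assumed q and an idealised model. Correct; they show direction and range only.

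Fourth, safety procedures may be written in documents not available here, such as the suicide protocol that Patient Safety mentions. That is possible. If a standard AE form exists there, the protocol should cite it.

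Three further inferences are tempting but unsupported:

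- The SAE examples, including "hospitalization due to worsening depressive symptoms or suicidal ideation", are introduced as what SAEs may include and also name life-threatening events. They do not show that a suicide attempt would be classed as non-serious.
- No section says that staff who know the arm judge the cause of an admission.
- The 30% attrition allowance is not differential by arm, and participants who stop treatment may continue assessments, so it does not support a bias between arms. Whether chart data are collected when a session is missed is simply not stated.

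**Conclusion.** The point holds as a risk of differential ascertainment. The only stated AE route runs through trained research staff, who treat BA-PC participants and not TAU participants: up to 10 scheduled contacts versus 6 by week 12. No standard question or AE-directed chart search offsets this. The likely direction is over-reporting in BA-PC, chiefly of physical and non-serious events.

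The contact count follows from the schedule, assuming full session attendance and no AE reporting from TAU sessions. The size of any distortion cannot be derived from the documents; the illustrative ratio of 1.5 to 1.0 depends wholly on the assumed q of 0.05 to 0.50. The primary PHQ-9 comparison is not affected. This is a cheap improvement to safety monitoring, not evidence that the trial's safety data are already biased.

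**What to change.** 1. Add one short, identical AE/SAE question set to the existing blinded assessments at weeks 2 to 12 and week 24.
2. Add hospitalisations, emergency visits, suicide attempts and death to the chart review already planned at weeks 12 and 24. Do this for every randomised participant, whether or not the session is attended.
3. Record the source of each event: assessment, chart, BA-PC session or other.
4. Base any by-arm AE comparison shown to the DSMB on sources 1 and 2, and list events learned only in BA-PC sessions separately. All events still go through the existing reporting channels.

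Cost: a protocol amendment, a few extra minutes per contact and a few more chart fields. More unrelated events will be recorded.
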